5.6 Creating Participant Folders

The fieldworker needs to be aware of the hard-copy documents which each of these folders will consist of so that if any hard-copy forms are missing from a folder or more hard-copy forms are needed they would be able to identify which forms are left out or are needed.

The fieldworker will be required to allocate a participant ID number to each of the folders and hard-copy forms by means of a participant ID sticker.

5.6.1. Participant EVERYDAY Folders

The EVERYDAY folder will contain all non-identifying hard-copy forms, i.e.:

- ✓ Participant Screener (hard copy available in English, IsiXhosa and Afrikaans)
- ✓ Baseline Assessment (hard copy available in English, IsiXhosa and Afrikaans)
- ✓ Appointment Cards
- ✓ Follow-Up Assessments (hard copy available in English, IsiXhosa and Afrikaans)
- ✓ Fetal/Birth/Neonatal Outcomes Form

Information and materials which will be included in the EVERYDAY folder and may possibly be given to the participant at the end of the first appointment:

- ✓ Referral Guide Hand-out
- ✓ MaRISA Contacts & Rights Cards (available in English, Afrikaans and IsiXhosa)
- ✓ MaRISA Appointment Cards (one for each consecutive appointment)

5.6.2. Participant CONTACT Folders

The CONTACT folder will contain all identifying hard-copy forms, i.e.:

- ✓ Information and Consent Form (available in English, IsiXhosa and Afrikaans)
- ✓ Contact Information Form (hard copy)
- ✓ MaRISA Specimen Collection Log
- ✓ Participant Locator Form (hard copy)
- ✓ Referral Form (hard copy)
- ✓ And/or any other document containing identifying information e.g., copies of receipts for transport fee received; etc.

CHAPTER 6: DISTRESSED RESPONDENTS

6.1 Introduction

Given the nature of this study, there may be instances, where you are faced with a distressed participant who you are concerned needs additional mental health support. For the most part, you can address this by talking to the participant and providing them with a referral to see the mental health nurse or for additional substance abuse services.

6.1. What is a distressed participant?

By “distressed” we mean that a participant shows signs of experiencing negative emotions and by her words, expressions, or other nonverbal behaviors or body language indicates that she is emotionally upset.

Possible signs or indications of distress:

- A participant who is tearful and/or reports that she feels badly or is sad.
- A participant who shows signs of being considerably more nervous or anxious (e.g., very nervous speech, increased sweating, difficulty sitting still during the appointment) than would be expected during an appointment.
- A participant who seems agitated or aggressive and that you cannot easily calm down.

6.1.1. Steps to follow with mildly distressed participants who need additional services.

In most cases of distress, participants may talk about feeling badly but you will be able to manage or contain these feelings and continue with the appointment. They may, however, need additional services or support once all study appointments have been completed.

In these cases, complete the following steps at the end of the study appointment:

- Indicate to the person that they seem upset or anxious.
- Discuss with the participant the importance of additional support.
- Ask if they would like to receive additional services to talk more about feelings that came up during the course of the study.

- If the participant indicates she would like to talk with someone further, ask if they would like you to refer them to an organization.
- Complete the referral and release form.
- With the patient's permission, call the agency or the mental health nurse to make an appointment.
- Provide the patient with a copy of the referral letter in an envelope and keep one in the CONTACTS folder.
- Provide the patient with a copy of our resource guide for additional services.
- If the participant indicates that she does not want you to make a direct referral, suggest various organizations for her to contact on her own and give them a copy of the resource guide.

These steps should only be followed if the participant shows signs of distress or expresses a need for further support - but **no suicidal intent or imminent harm is disclosed or suspected.**

If the person expresses any desire to end their life or hurt themselves or others, follow the steps described in 6.2.

6.1.2. Steps to follow with very distressed participants.

There may be instances where participants are so distressed that you are concerned for their safety and may not be able to continue with the appointment. Remember that we have made it clear in the consent form that there are exceptions to our promise of confidentiality. If participants express the intent to harm themselves or others, or ongoing abuse and/or neglect of children, then we have a duty to report this matter to the proper authorities, e.g., the police, courts or social workers. Field staff will provide information on toll-free hotlines that people can call to talk to someone and seek assistance, as well as local resource information.

If during the study you are concerned that a participant intends to harm herself or others, then mandatory reporting procedures need to be followed on completion of the appointment. Immediately inform the Project Coordinator and the Site PI, who will report the mandatory reporting incidents to the ethics committee and our project officer within 72 hours.

In these instances, please follow the following steps:

- As far as possible, complete the study appointment.
- Indicate to the person that they seem upset or anxious.
- If they are expressing a desire to end their life (suicide), explore further whether this is an expression of distress or whether they have a) had previous attempts, b) have a plan to end their life.
- If there is immediacy and a plan for suicide, remind the person of the limits of confidentiality as expressed in the consent form, and your duty to report.
- Follow the mandatory reporting procedures described below.
- Complete the referral and release form
- Call the the mental health nurse to make an immediate appointment or accompany the participant to the ER section of the healthcare facility.
- Provide the patients with a copy of the referral letter in an envelope and keep one in the CONTACTS folder.
- Provide the patient with a copy of our resource guide for additional services.
- Follow the reporting procedures in Chapter 7- complete an incident report form and immediately send to the Project Coordinator and Site PI who will both keep copies on file.

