6.2. Mandatory reporting procedures

It is possible that a participant will indicate during the course of a discussion that she is in immediate danger of harm or poses a threat to the safety of others. We want you to feel that you can handle this situation with confidence.

There are essentially three situations in which there may be immediate danger of harm:

- 1) **Suicidal Intent:** The participant expresses a desire to hurt or kill themselves.
- 2) **Hurtful Intent to Others:** The participant expresses an interest in hurting or killing someone else (not necessarily someone living in the household).
- 3) **Child Abuse and Neglect:** Ongoing abuse and/or neglect of children.

For each of these cases, you must follow compulsory or mandatory reporting procedures.

These procedures are important to follow because they take away the responsibility of you having to decide what to do. These procedures are in your best interest and in the best interest of the participant- they are there to keep the participant safe and unharmed.

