6.2.1. Suicidal Intent

If a participant expresses an interest in harming or killing herself, assess whether the risk is immediate or not immediate.

Assessing immediacy of risk for suicide: Assessing risk for suicide involves exploring whether the person has current suicidal thoughts, a plan for suicide and access to means. Assess the risk asking the following questions:

		In The Past Month	
Answer Questions 1 and 2		YES	NO
1) Have you wished you were dead or wished you could go to sleep and not wake up?			
2) Have you actually had any thoughts about killing yourself?			
If YES to 2, answer questions 3, 4, 5, and 6. If NO to 2, go directly to question 6			
3) Have you thought about how you might do this?			
4) Have you had any intention of acting on these thoughts of killing yourself, as opposed to you have the thoughts but you definitely would not act on them?			
5) Have you started to work out or worked out the details of how to kill yourself? Do you intend to carry out this plan?			

In The Past Month	In the Past 3 Months

6) Have you done anything, started to do anything, or prepared to do anything to end your life?
 
Examples: Collected pills, obtained a gun, gave away valuables, wrote a will or suicide note, took out pills but didn't swallow any, held a gun but changed your mind or it was grabbed from your hand, went to the roof but didn't jump; or actually took pills, tried to shoot yourself, cut yourself, tried to hang yourself, etc.
 
In your entire lifetime, how many times have you done any of these things?
	

If the person answers YES to either questions 4, 5, or 6, this is a red flag, and you should consider them at high risk for suicide. Risk is not immediate if the person is expressing some suicidal thoughts to describe how badly they feel but they do not have a plan.

Note: A suicide plan or preparation for death, such as saying goodbyes and putting affairs in order, indicates serious suicidal intent!

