6.2.2. Hurtful Intent to Others

It is extremely unlikely, but someone may spontaneously tell you that they are planning to seriously hurt or kill someone else. If a participant expresses an interest in harming or killing someone else, you should take the following steps.

- As far as possible, complete the study appointment.
- Indicate to the person that they seem upset.
- If they are expressing a desire to hurt someone else, explore whether there is an immediate risk (i.e., they have a plan and the means to do it).
- If there is immediacy and a plan, remind the person of the limits of confidentiality as expressed in the consent form, and your duty to report.
- Follow the mandatory reporting procedures described in Chapter 7.
- Complete an incident report form and immediately send to the Project Coordinator and Site PI who will both keep copies on file.

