6.2.3. Child Abuse/Neglect

It is extremely unlikely, but someone may tell you that s/he has abused or neglected a child. If a participant reports this, you must report the incident to the police (if sexual abuse), or Childline (if any other type of abuse) after completing the appointment.

Follow these steps:

- As far as possible, complete the study appointment.
- Indicate to the person that they seem upset.
- If they are reported abusing a child, remind the person of the limits of confidentiality as expressed in the consent form, and your duty to report.
- Follow the reporting procedures in Chapter 7- complete an incident report form and immediately send to the Project Coordinator and Site PI who will both keep copies on file.

CHAPTER 7: INCIDENT REPORTING

7. Introduction

This chapter will outline the various types of reporting that may take place, and under which circumstances they should occur.

Although the proposed study presents no greater than minimal risk to participants, adequate provisions to mitigate these risks will be outlined further in this chapter.

The potential risks to participants include:

- 1) lack of comprehension and acknowledgement of informed consent, study purpose, and rights of participants;
- 2) exposure to psychological or physical coercion by clinical staff and others;
- 3) possible disclosure of confidential information;
- 4) the possible mental discomfort associated with some of the sensitive issues raised during assessments and biological specimen collection and results; and
- 5) social ramifications of participation in the study.

7.1. **Incident Reporting**

Incidents are defined as untoward events that occur during conduct of research projects and that affect research participants or staff or may affect study progress.

It is the responsibility of study staff who becomes aware of incidents to report them promptly so that they can be evaluated, reported and responded to appropriately by the study management. Depending on what has occurred, a reported incident may also qualify as an adverse event (AE) or serious adverse event (SAE), social harm, protocol deviation, and/or require reporting to civil authorities.

Examples of incidents that might occur during the study and should be reported include:

- a participant becomes violent towards a staff member.

- a participant reports to a fieldworker that she has suffered abuse from her husband because of her participation in the study or intervention.

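### The manual orders its safety steps inconsistently, and the child-abuse procedure puts the outside report after the appointment with no exception for immediate danger

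*Protocol*

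**What the plan says.** Protocol 6.2 introduces its subject with the words "There are essentially three situations in which there may be immediate danger of harm" and names suicidal intent, intent to hurt others, and ongoing child abuse or neglect.

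- **6.1.2 (very distressed participants).** Where staff fear that a participant intends to harm herself or others, "mandatory reporting procedures need to be followed on completion of the appointment". The next sentence reads "Immediately inform the Project Coordinator and the Site PI". The first listed step is "As far as possible, complete the study appointment". The section also recognises that staff "may not be able to continue with the appointment".
- **6.2.1 (suicidal intent).** "If a participant expresses an interest in harming or killing herself, assess whether the risk is immediate or not immediate". Completing the appointment is listed under 6.2.1.1, for no immediate risk. It does not appear under 6.2.1.2, for immediate risk.
- **6.2.2 (harm to others).** The first step is the same completion step as in 6.1.2. The third is "If they are expressing a desire to hurt someone else, explore whether there is an immediate risk". Under 6.2.2.2, perceived immediate danger calls for an immediate alert to the Project Coordinator and Site PI.
- **6.2.3 (child abuse or neglect).** Staff must report to the police if the abuse is sexual, "or Childline (if any other type of abuse) after completing the appointment". The completion step again comes first, and there are no separate branches for immediate and non-immediate risk.

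**The concern.** A fieldworker who follows 6.1.2 or 6.2.2 in the order listed could finish a questionnaire before finding out whether harm is imminent. One who follows 6.2.3 could finish it before reporting a child in danger to an outside body. What is at stake is the safety of the participant, of third parties and of children.

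Disclosure is foreseeable. Under 5.3 the baseline questions cover violence exposure, coping with stress and mental health, and 7.1.2 describes the participants as at risk of postpartum depression and clinical worsening. Section 5.2 excludes women with current suicidal thoughts, or attempts in the past month, so the suicide procedure matters mainly for later disclosures. Intent to harm others and child abuse are not among the listed exclusions. Women enter while pregnant or up to three months postpartum, so the child concerned could be an infant.

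**Working it through.** No figure is involved, so the check sets the step orders side by side.

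| Section | First listed step | Where immediacy is checked | Timing of the report | Immediate-risk branch |
|---|---|---|---|---|
| 6.1.2 | Complete the appointment, if feasible | Third and fourth steps (suicide plan) | After the appointment, stated in a sentence; internal notice immediate | None of its own; points on to 6.2 |
| 6.2.1 | Assess immediacy | First | Incident report after the steps if there is no immediate risk; crisis-line offer at once if there is | Yes, without a completion step |
| 6.2.2 | Complete the appointment, if feasible | Third step (plan and means) | No timing sentence; order of unnumbered steps only | Yes, 6.2.2.2, without a completion step |
| 6.2.3 | Complete the appointment, if feasible | Not checked | After the appointment, stated in a sentence | No |

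**Suicidal intent.** Sections 6.1.2 and 6.2.1 give different orders for the same disclosure. The closing line of 6.1.1 sends any wish to harm oneself or others to 6.2, and 6.1.2 itself refers forward to the reporting procedures. A reader who follows those pointers reaches 6.2.1, where completion depends on there being no immediate risk. A reader who stays in 6.1.2 is told to complete first. The timing sentence in 6.1.2 carries no feasibility qualifier; only the list step does.

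**Harm to others.** The same pointer leads to 6.2.2, where completion is again listed first. The alert in 6.2.2.2 depends on danger being perceived, but the step that looks for a plan and means comes after completion. Danger that is obvious from the disclosure is covered. Danger that only the plan-and-means questions would reveal could be found late.

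**Child abuse or neglect.** Nothing in 6.2.3 shortens the wait. Section 7.1 lists child abuse in the home as an incident, and 7.2 asks for an immediate verbal report of incidents to the Project Coordinator. Together with the immediate notice in 6.1.2, this speeds internal notice. It does not alter the timing that 6.2.3 sets for the police or Childline.

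**General text elsewhere.** Section 3.1 in Chapter 4 tells staff to stop an interview when a participant becomes unwilling or upset, and to call medical staff if she seems unwell. It addresses the participant's own condition, not danger to a third party or a child. Section 2.5.2 deals with mental-status concerns before an appointment begins.

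**Count.** Of the three situations in 6.2, one has immediacy first (suicide), one has completion listed first but an immediate-alert branch (harm to others), and one has completion first and no such branch (child abuse).

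**The case against.** The strongest reply is that the manual already protects against the danger. Each of the three completion steps is softened by a feasibility qualifier. Section 6.1.2 expects that some appointments will stop, requires immediate notice to senior staff, and provides for an immediate mental-health appointment or an escort to the emergency room. Sections 6.2.1.2 and 6.2.2.2 contain no completion step, and both keep the participant from leaving alone or before instructions arrive. Section 6.2.3 makes the child-abuse report compulsory at any level of risk, so the missing branch cannot cause a report to be missed. At most the report waits for the rest of one appointment.

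Much of this stands, and it rules out three stronger readings that a reader might infer:

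- That nothing in the manual lets immediate risk override completion. For suicide, 6.2.1 does so in substance by keeping completion for no immediate risk. For harm to others, 6.2.2.2 calls for action as soon as danger is perceived.
- That three of four independent procedures put completion first. Section 6.1.2 refers on to 6.2 and is not a separate fourth route.
- That escalation within the study team is delayed. Sections 6.1.2 and 7.2 both ask for immediate notice.

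The reply does not remove the conflict between 6.1.2 and 6.2.1, the position of the risk check in 6.2.2, or the unqualified timing in 6.2.3. Section 6.2 says that its procedures spare staff from having to decide what to do. A manual with that aim should not leave them to infer which step gives way. A calm participant who discloses a plan and is able to finish the questionnaire is not covered by the wording on being unable to continue.

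**Conclusion.** The concern holds as an inconsistency in safety instructions, with one clear gap. Sections 6.1.2 and 6.2.1 conflict on order for suicidal intent. Section 6.2.2 places its risk check after completion, although 6.2.2.2 partly makes up for this. Section 6.2.3 sets the outside report after the appointment with no exception for immediate danger, and this is the most important of the three.

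The conclusion assumes that fieldworkers read the lists as sequences. For 6.1.2 and 6.2.3 it also rests on stated timing sentences; for 6.2.2 it rests on list order alone. The procedures can apply at any of the three assessments per woman or at the twice-weekly urine visits, but the documents give no disclosure rate and no length for the remaining appointment, so neither a frequency nor a delay is claimed. No endpoint, sample size or analysis in the SAP is touched. The manual should be changed because the possible harm is serious and the safer order already exists in 6.2.1.

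**What to change.** 1. In 6.1.2 and 6.2.2, make the first step an assessment of immediacy as soon as intent is disclosed, using the 6.2.1 questions for suicide and the 6.2.2 plan-and-means check for harm to others.
2. If risk is immediate, pause the appointment and go to 6.2.1.2 or 6.2.2.2. If it is not, complete the appointment as far as is feasible and then report, keeping the immediate internal notice in 6.1.2 and 6.2.2.1.
3. State in 6.1.2 that the timing sentence does not apply to immediate risk.
4. Add to 6.2.3 that, if a child is in immediate danger, staff pause the appointment, alert the Project Coordinator and Site PI, and make the outside report at once.

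The cost is rewording three step lists and two timing sentences, documentation and ethics approval of the change as Chapter 4 (Potential Improvements) provides, and a short re-briefing of the Project Coordinator and the two fieldworkers. An assessment may occasionally be interrupted, and its remaining items would then be rescheduled or missing. The analysis plan does not change.

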6.2. Mandatory reporting procedures

It is possible that a participant will indicate during the course of a discussion that she is in immediate danger of harm or poses a threat to the safety of others. We want you to feel that you can handle this situation with confidence.

There are essentially three situations in which there may be immediate danger of harm:

- 1) **Suicidal Intent:** The participant expresses a desire to hurt or kill themselves.
- 2) **Hurtful Intent to Others:** The participant expresses an interest in hurting or killing someone else (not necessarily someone living in the household).
- 3) **Child Abuse and Neglect:** Ongoing abuse and/or neglect of children.

For each of these cases, you must follow compulsory or mandatory reporting procedures.

These procedures are important to follow because they take away the responsibility of you having to decide what to do. These procedures are in your best interest and in the best interest of the participant- they are there to keep the participant safe and unharmed.

6.2.1. Suicidal Intent

If a participant expresses an interest in harming or killing herself, assess whether the risk is immediate or not immediate.

Assessing immediacy of risk for suicide: Assessing risk for suicide involves exploring whether the person has current suicidal thoughts, a plan for suicide and access to means. Assess the risk asking the following questions:

		In The Past Month	
Answer Questions 1 and 2		YES	NO
1) Have you wished you were dead or wished you could go to sleep and not wake up?			
2) Have you actually had any thoughts about killing yourself?			
If YES to 2, answer questions 3, 4, 5, and 6. If NO to 2, go directly to question 6			
3) Have you thought about how you might do this?			
4) Have you had any intention of acting on these thoughts of killing yourself, as opposed to you have the thoughts but you definitely would not act on them?			
5) Have you started to work out or worked out the details of how to kill yourself? Do you intend to carry out this plan?			

In The Past Month	In the Past 3 Months

6) Have you done anything, started to do anything, or prepared to do anything to end your life?
 
Examples: Collected pills, obtained a gun, gave away valuables, wrote a will or suicide note, took out pills but didn't swallow any, held a gun but changed your mind or it was grabbed from your hand, went to the roof but didn't jump; or actually took pills, tried to shoot yourself, cut yourself, tried to hang yourself, etc.
 
In your entire lifetime, how many times have you done any of these things?
	

If the person answers YES to either questions 4, 5, or 6, this is a red flag, and you should consider them at high risk for suicide. Risk is not immediate if the person is expressing some suicidal thoughts to describe how badly they feel but they do not have a plan.

Note: A suicide plan or preparation for death, such as saying goodbyes and putting affairs in order, indicates serious suicidal intent!

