6.2.1.1. Procedure: NO IMMEDIATE RISK

If it is clear to you that the participant poses no immediate risk to herself (i.e., the participant is not currently suicidal, but alluded to self-harm for some other reason, for example, to express how difficult their life circumstances are), then you should do the following:

- Complete the appointment,
- Remind participant of limits to confidentiality from the "Participant Information and Consent Form" and discuss seeking help by contacting LifeLine, SADAG or the Mental Health Nurse,

c) After following these steps, you should complete an incident report form and report the incident to the Project Coordinator. Chapter 7 describes the reporting process in more detail.

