6.2.1.2. Procedure: IMMEDIATE RISK

If you assess that the participant is at **immediate risk** to herself, read the following script to the participant:

Script: Risk of participant suicide or self-injury (immediate danger of harm)

Team member reads:

"When you agreed to participate in this study, I promised that I would tell someone what you told me only if it was necessary to protect you or other people. You told me earlier that you were thinking of harming yourself. I suggest we contact an organization called LifeLine or SADAG and let them know so they can talk to you about how you feel. LifeLine and SADAG offers counseling. You can discuss your problem with one of their counsellors and they may be able to help you. Do you want to call them, or should I call them for you?"

Willing participant:

- If the participant agrees to contact Lifeline or SADAG, use the project phone to make the call for the participant, hand them the phone and go to another room to give them privacy during the call.
- If the participant asks you to make the call on their behalf, use the project phone to make the call for the participant, hand the phone to the participant and go to another room to give them privacy in the call.

Unwilling participant

- If the participant is unwilling to contact the crisis hotline and doesn't want you to contact them, then you should immediately contact the Project Coordinator/Site PI, who can assess the situation (e.g., determine reasons why the participant is unwilling to contact the hotline so these issues can be addressed) and who can contact one of the psychologists in the investigative team for further inputs.

- You can also contact the family physician and/or mental health nurse at the facility for their guidance.
- In the meantime, do not leave the participant by herself nor let them leave on their own, as they pose a risk to themselves.
- Ask the participant if she has a close family member or friend who can come to sit with them until you receive clear instructions about what to do.
- If the participant remains unwilling to contact the hotline, provide the participant with the referral guide as well as the counselling hotline numbers.
- Make sure you document who you spoke to, and the advice provided on the incident form (see Chapter 7)

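### Section 6.2.1 grades suicide risk on two unlinked scales, so a woman flagged as high risk without a stated plan can be read into the weaker procedure

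*Protocol*

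**What the plan says.** Section 6.2.1 sets the fieldworker a two-way task: "If a participant expresses an interest in harming or killing herself, assess whether the risk is immediate or not immediate". Six questions follow, under a lead-in about judging how immediate the risk is. Question 2 asks about thoughts of suicide, 3 about method, 4 about intention, 5 about a plan, and 6 about acts or preparation. There is one skip rule: "If NO to 2, go directly to question 6".

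Two rules for reading the answers come next. The first covers a YES to any of three questions: "questions 4, 5, or 6, this is a red flag, and you should consider them at high risk for suicide". The second is: "Risk is not immediate if the person is expressing some suicidal thoughts to describe how badly they feel but they do not have a plan". A note adds: "A suicide plan or preparation for death, such as saying goodbyes and putting affairs in order, indicates serious suicidal intent".

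There are two procedures.

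- **6.2.1.1 (no immediate risk)** applies when the absence of immediate risk is clear to the fieldworker. The example is a case where "the participant is not currently suicidal, but alluded to self-harm for some other reason". Staff finish the appointment, restate the limits of confidentiality and "discuss seeking help by contacting LifeLine, SADAG or the Mental Health Nurse". They then complete an incident form and report to the Project Coordinator.
- **6.2.1.2 (immediate risk)** applies when the fieldworker assesses the risk as immediate. A script that includes "You told me earlier that you were thinking of harming yourself" leads to an offer to call a counselling line on the project phone. If the woman declines, staff contact the Project Coordinator or Site PI and do not leave her alone.

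Section 6.1.2, on very distressed participants, applies when staff are concerned that a woman intends to harm herself or others. It has staff inform the Project Coordinator and Site PI at once, and either arrange an immediate mental health nurse appointment or accompany her to the emergency room.

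**The concern.** The answers yield one label (high risk) and the procedures need another (immediate). No sentence connects them. The only text in 6.2.1 that bears on the second label turns on whether there is a plan, which the first label does not require. In 6.1.2, too, the reminder about the limits of confidentiality is tied to immediacy together with a plan.

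A fieldworker who has just recorded a stated intention, or recent preparation, with no plan therefore has to choose the procedure unaided. Section 6.2 says that the procedures exist to spare staff that choice, and the fieldworker duties in section 2.2.2 are screening, consent, assessment and tracking.

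The choice has consequences. Under 6.2.1.2 a hotline call is offered on the spot, and a woman who refuses is not left alone. Under 6.2.1.1 she has a conversation about seeking help and the incident is reported.

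Screening does not remove these cases. Section 5.2 excludes current suicidal thoughts and attempts in the past month. Question 6 also covers preparation and carries a 3-month column, and risk can arise during follow-up, which runs to 3 months.

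**Working it through.** The plan gives no figure to reproduce, so the check compares the rules with every answer pattern that the form allows.

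**Inputs**, all from section 6.2.1 and its two procedures: the skip rule after question 2, the high-risk rule (YES to 4, 5 or 6), the not-immediate sentence, and the entry wording of 6.2.1.1 and 6.2.1.2. Question 1 is left out because it routes nothing.

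**Possible patterns.** With YES to 2, questions 3 to 6 are each YES or NO: 2 × 2 × 2 × 2 = 16. With NO to 2, only question 6 remains: 2. Total: 16 + 2 = 18.

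**High-risk patterns.** With YES to 2, questions 4 to 6 have 2 × 2 × 2 − 1 = 7 combinations with at least one YES. Each occurs with YES or NO to question 3: 7 × 2 = 14. With NO to 2, only YES to 6 counts: 1. Total: 14 + 1 = 15.

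| Answers | Patterns | High risk? | Against the not-immediate sentence | Procedure named for these answers |
|---|---|---|---|---|
| YES to 2, YES to 5 | 8 | yes | falls outside it: there is a plan | none; 6.2.1.2 by inference |
| YES to 2, NO to 5, YES to 4 and/or 6 | 6 | yes | no-plan half met; the other half is judgement | none |
| NO to 2, YES to 6 | 1 | yes | plan never asked | none |
| YES to 2, NO to 4, 5 and 6 | 2 | no | no-plan half met; the other half is judgement | none; 6.2.1.1 only if clear |
| NO to 2, NO to 6 | 1 | no | plan never asked | none; 6.2.1.1 only if clear |

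Check: 8 + 6 + 1 + 2 + 1 = 18, and 8 + 6 + 1 = 15 are high risk.

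**Result.** 6 + 1 = 7 of the 15 high-risk patterns have no YES to the plan question. For these, the first rule signals danger, and the second either leans towards the weaker procedure or cannot be applied. The 8 patterns with a plan are not expressly mapped either, but inference from the second rule and the note points them to 6.2.1.2.

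**The single NO-to-2 pattern.** She reaches question 6 without being asked about intention or plan. A literal reader may take her denial of suicidal thoughts as matching the example in 6.2.1.1, although by the manual's own rule she is high risk. For her the hazard is being sent the wrong way. She should not be described as having answered NO to question 5.

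**The case against.** The strongest reply is that a sensible reader would get this right. The six questions stand under the lead-in about immediacy, so a red flag is most naturally a positive result of that assessment. The not-immediate sentence needs both parts: no plan, and thoughts voiced only to convey distress. Section 6.2.1.1 is open only when the absence of immediate risk is clear, which is hard to claim after a stated intention. The note treats preparation as serious intent. The nurse or emergency room step in 6.1.2 has no plan condition. Even 6.2.1.1 requires a report to the Project Coordinator, and under 7.1.1 and 7.2 suicidal ideation is at least an adverse event to be reported verbally at once.

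Most of this stands, and it rules out several stronger readings that a reader might infer:

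- **That these women have no procedure at all.** The fieldworker must still choose one of two classes. The defect is an undefined and conflicting rule for choosing.
- **That the NO-to-2 woman is shown to be the least protected.** The documents do not rank cases. She is a plausible weak spot, no more.
- **That the 6.2.1.2 script cannot be used for her.** Section 6.2.1 is entered only after a woman has voiced an interest in self-harm, so the script broadly fits.
- **That she would leave after a conversation and nothing else.** Reporting is required on either route, and 6.1.2 may apply as well.

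The reply does not supply the missing link. The lead-in is not carried into either procedure, the note names no procedure, and 6.1.2 depends on staff already being concerned about intent. Section 6.1.1 sends a mildly distressed woman who voices a wish to die or to hurt herself directly to 6.2, without requiring 6.1.2. In 6.2.1.2 itself, contact with the nurse is optional and listed only for an unwilling participant.

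**Conclusion.** The concern holds as a conflict between two stated rules. YES to 4, 5 or 6 means high risk with or without a plan. The procedures depend on an undefined immediacy that the next sentence links to having a plan. A woman with YES to 4 or 6 and no stated plan, including one with NO to 2, can be read into 6.2.1.1. The clear-risk condition, the note and section 6.1.2 make this less likely but do not exclude it.

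The extent is 7 of 15 high-risk answer patterns. That is a count of form entries and must not be taken as a proportion of women. The documents give no rate of suicidal disclosure, so the number affected is bounded only by 0 and the 60 planned. The assumption here is that it is small, because the questions are asked only after a woman voices an interest in self-harm.

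Two further assumptions matter. One is that some fieldworkers will apply the text literally. The other is that the 3-month column belongs to question 6: past-month, 3-month and lifetime wording all appear around that question, and the table may have been split in extraction.

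This is a participant-safety point that should be corrected. No endpoint or analysis is affected.

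**What to change.** After the high-risk sentence in 6.2.1, add:

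> Treat YES to 4 or 5, or YES to 6 within the past 3 months, as immediate risk, with or without a plan: follow 6.2.1.2 and the mental health nurse/ER step in 6.1.2. For all other answers, follow 6.2.1.1 only if it is clear that there is no immediate risk; if in doubt, follow 6.2.1.2.

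This assigns all 15 high-risk patterns, provided that any YES to 6 standing alone falls within the window. The other 3 of the 18 stay under the existing clear-risk test. The second sentence should not be shortened to send everyone else to 6.2.1.1. A woman with current thoughts and a method (YES to 2 and 3, NO to 4, 5 and 6) would then go to the weaker procedure by rule, with less protection than the present text gives her.

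The investigators should confirm the question 6 time window against the printed form before adopting the 3-month limit.

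The cost is two sentences and a brief retraining note, with no new data collection. The downside is a few extra hotline offers or same-day nurse contacts, some for women with recent behaviour but no current thoughts.
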